6.1 Safety and Reactogenicity Assessments

Safety will be assessed through the collection and evaluation of solicited and unsolicited AEs, MAAEs, SAEs, and AESIs. Safety will also be assessed based on physical examinations, vital sign measurements, and clinical laboratory assessments. Refer to the SOE table in Appendix 13.1 for assessment time points and a full list of visit and assessments (Table 13-1).

All suspected cases of COVID-19 in study participants will be diagnosed and clinically evaluated, which require unscheduled study site visits and additional SARS-CoV-2 laboratory testing.

Any abnormal laboratory test results or other safety assessments (eg, physical examinations, vital sign measurements), including those that worsen from baseline or are clinically significant in the medical and scientific judgment of the investigator, are to be recorded as AEs or SAEs as applicable.

6.1.1 Adverse Events

6.1.1.1 Definitions

6.1.1.1.1 Adverse Events

The investigator is responsible for reporting all AEs that are observed or reported during the study, regardless of their relationship to the IP or their clinical significance.

An AE is defined as any untoward medical occurrence in a participant enrolled into this study regardless of its causal relationship to the IP. Participants will be instructed to contact the investigator at any time after enrollment if any symptoms develop.

A solicited AE is defined as an AE that is reported with onset within 7 days of study vaccination (Days 1 to 7), as recorded by participants in an eDiary (Section 6.1.1.5). After study vaccination all participants will be instructed to record selected local and systemic postvaccination reactions (solicited AEs) in an eDiary. Local solicited AEs will include injection site pain, redness, swelling, and lymphadenopathy. Systemic solicited events will include fever, headache, fatigue, myalgia, arthralgia, and chills. Solicited local and systemic AEs will be used to assess reactogenicity and will be assigned a grade as described in Section 6.1.1.2.1. Any such AEs reported after the 7-day window will be reported as unsolicited AEs.

An unsolicited AE is defined as any AE that is volunteered from the participant and occurs within 28 days after vaccination.

An MAAE is defined as an AE that results in a visit to a medical professional. Medically attended visits are defined as a telemedicine visit, physician's office visit, urgent care visit, emergency room visit, hospitalization, or death.

6.1.1.1.2 Serious Adverse Events

An SAE is defined as any event that:

- Results in death
- Is immediately life-threatening
- Requires inpatient hospitalization or prolongation of existing hospitalization
- Results in persistent or significant disability/incapacity
- Is a congenital anomaly/birth defect
- Is a spontaneous miscarriage (see also Section 6.2)

Important medical events that may not result in death, be life-threatening, or require hospitalization may be considered SAEs when, based upon appropriate medical judgment, they may jeopardize the participant or may require medical or surgical intervention to prevent one of the outcomes listed in this definition. Examples of such medical events include allergic bronchospasm requiring intensive treatment in an emergency room or at home, blood dyscrasias or convulsions that do not result in inpatient hospitalization, or the development of drug dependency or drug abuse.

6.1.1.1.3 Suspected Unexpected Serious Adverse Reactions

A SUSAR is defined as an adverse reaction, the nature or severity of which is not consistent with the applicable product information (eg, IB for an unapproved IP).

6.1.1.1.4 Adverse Events of Special Interest

An AESI (serious or nonserious) is defined as an AE or SAE of scientific and medical concern specific to the sponsor's product or program, for which ongoing monitoring and rapid communication by the investigator to the sponsor could be appropriate (ICH E2F; CIOMS VI).

For this study, AESIs will include the following events:

- Virologically confirmed SARS-CoV-2 infections (see Section 6.6 for disease definitions)
- Potential immune-mediated disorders (Appendix 13.4)
- Anaphylaxis or severe hypersensitivity within 24 hours after study vaccine administration
- Pericarditis or myocarditis

Refer to Section 6.1.1.3.1 for reporting AESIs.

6.1.1.2 Eliciting and Documenting Adverse Events

Adverse events will be reported throughout the study. Nonserious AEs will be reported from the time of the administration of IP until 28 days after the administration of IP; SAEs will be reported from the time the participant signs the ICF until exit from the study.

If the investigator learns of any SAE, including a death, at any time after a participant has been discharged from the study, and he/she considers the event to be reasonably related to the IP, the investigator must notify PPD Pharmacovigilance within 24 hours of learning of the event (Section 6.1.1.3.1).

At every study visit, participants will be asked a standard nonleading question to elicit any medically related changes in their well-being.

In addition to participant observations, AEs identified from any study data (eg, laboratory values, physical examination findings) or identified from review of other documents (eg, participant eDiaries) that are relevant to participant safety will be documented on the AE page in the eCRF.

As described in Section 6.1.1.1.1, participant eDiaries will be used to collect solicited AEs.

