• Participants with medically documented risk factors for severe COVID-19 disease will be excluded from the study and the occurrence of 2 cases of severe COVID-19 disease will trigger the hold of the whole Phase 1 study.

Participants will receive close medical supervision and medical assessments (eg, laboratory testing) during the study.

The investigational CV2CoV vaccine is currently in an early stage of clinical development and vaccine efficacy, immunogenicity, and safety have not yet been demonstrated in humans. Considering the risk mitigation strategies, measures taken, and planned to be taken to minimize risk to participants in this Phase 1 clinical trial, the potential risks associated with the investigational vaccines are considered acceptable.

2 Study Objectives and Endpoints

The study objectives and endpoints are described in Table 2-1.

Table 2-1 Study Objectives and Endpoints

Objectives	Endpoints				
Primary – Safety					
To evaluate the safety and reactogenicity of CV2CoV at each dose level in SARS-CoV-2 seropositive healthy adult participants after booster vaccination	Percentage of participants with MAAEs, SAEs, and AESIs from study vaccination through the end of the study (approximately 180 days after the study vaccine administration), each summarized separately				
	Percentage of participants with each solicited local and systemic AE within the 7-day postvaccination period (Days 1 to 7)				
	Percentage of participants with unsolicited AEs up to 28 days after study vaccination, including clinically relevant abnormal laboratory findings				
Secondary – Immunogenicity					
To explore the dose response and effect of CV2CoV at each dose level on neutralizing Ab titers against pseudovirus bearing spike protein from SARS-CoV-2 WT in SARS-CoV-2	GMTs of neutralizing Ab titers against pseudovirus bearing spike protein from either SARS-CoV-2 WT at each collection time point (Days 1, 8, 15, 29, 85, and 180)				
seropositive healthy adult participants after booster vaccination	• Percentage of participants with seroresponse (≥4-fold rise from baseline) at Day 29 after the booster dose				
	GMI from baseline of neutralizing Ab titers against pseudovirus bearing spike protein from SARS-CoV-2 WT at each collection time point (Days 8, 15, 29, 85, and 180)				

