6.1.1.3.1 Reporting Serious Adverse Events and Adverse Events of Special Interest

Any AE that meets SAE criteria (Section 6.1.1.1.2) must be reported to PPD Pharmacovigilance within 24 hours after site personnel first learn of the event. Events should be captured electronically in the EDC system; however, if the EDC is unavailable, a backup paper option is available and this form can be faxed to the fax number listed below.

SAE [contact] [contact]

Any AE that meets AESI criteria (Section 6.1.1.1.4) must be reported to PPD Pharmacovigilance within 24 hours after site personnel first learn of the event.

If the EDC is unavailable and a faxed form is used to report an SAE or AESI, the site should update the EDC with exactly the same information reported on paper (by fax) as soon as possible after the EDC becomes available again.

The sponsor has a legal responsibility to notify both the local regulatory authority and other regulatory agencies about the safety of an IP under clinical investigation. The sponsor will comply with country-specific regulatory requirements relating to safety reporting to the regulatory authority, IRB/IEC, and investigators.

An investigator who receives an investigator safety report describing an SAE or other specific safety information from the sponsor will review and then file it as appropriate and will notify the IRB/IEC according to local requirements.

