6.6 SARS-CoV-2 and COVID-19 Disease Assessment and Definitions

Vaccine efficacy will not be evaluated in this study, but all virologically confirmed SARS-CoV-2 infections should be reported by the participant and documented as clinical events as well as AESIs (Section 6.1.1.1.4). Any available isolate genotyping results will also be requested. Participants will be instructed to inform the investigator in the event of a positive SARS-CoV-2 diagnostic test. Clinical serology testing, including N protein, will be performed at Screening, Day 1, Day 85, and Day 180 to monitor for undetected SARS-CoV-2 infections. A nasal (nasopharyngeal or mid-turbinate) swab sample is scheduled for SARS-CoV-2 RT-PCR testing at Screening and Day 1. The screening sampling and SARS-CoV-2 RT-PCR testing must be performed within the 7 days before Day 1.

All participants with suspected COVID-19 are required to have an unscheduled visit for suspected COVID-19. At this visit, participants will undergo the following assessments:

- Medical history
- SARS-CoV-2 RT-PCR (nasal swab [nasopharyngeal or mid-turbinate])
- Physical examination
- Vital sign measurements
- Review of adverse events
- Concomitant medication/vaccination

All participants with confirmed COVID-19 are required to have an unscheduled COVID-19 convalescent visit. At this visit, participants will undergo the following assessments:

- Medical history
- Physical examination
- Vital sign measurements
- COVID-19 evaluation
- Review of adverse events
- Concomitant medication/vaccination

To complete the COVID-19 evaluation, the investigator will review the history of the participants, including medical records to define the severity of COVID-19. Any virologically confirmed cases of SARS-CoV-2 infection or COVID-19 during the study will be assigned one of the following definitions:

Asymptomatic	Virologically confirmed SARS-CoV-2 by RT-PCR or N protein
SARS-CoV-2	seroconversion without any of the following symptoms: fever or
infection:	chills, cough, shortness of breath or difficulty breathing, fatigue,
	muscle or body aches, headache, new loss of taste or smell, sore

throat, congestion or runny nose, nausea or vomiting, diarrhea

taste or smell, sore throat, congestion or runny nose, nausea or

Symptomatic Virologically confirmed by RT-PCR and include one or more of the COVID-19: following: fever or chills, cough, shortness of breath or difficulty breathing, fatigue, muscle or body aches, headache, new loss of

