- j. Clinical safety laboratory testing will include hematology and serum chemistry. Screening laboratory tests may be repeated once for enrollment requirements. HIV 1/2, HB surface antigen, and anti-HCV testing will be performed at Screening only. Unscheduled visit may occur for the evaluation and follow-up of any AE. At unscheduled visits, clinical safety laboratory testing will be done as per investigator decision.
- k. Blood draws for immunogenicity assessments (binding IgG and neutralization) after D29 will only be obtained from participants who have not yet received a COVID-19 booster vaccination with an authorized or licensed product.
- 1. Participants will be instructed to inform the investigator in the event of a positive SARS-CoV-2 diagnostic test. In this case, he/she will be invited to perform an unscheduled visit on site for COVID-19 evaluation according to the definitions provided in Section 6.6. All effort should be made by the investigator to ensure the disease assessment is performed in a timely manner versus the test results.
- m. Solicited local and systemic AEs will be collected during the 7 days after study vaccination (Days 1 to 7) via eDiaries. Unsolicited AEs will be recorded for 28 days after study vaccination. SAEs, MAAEs, and AESIs will be collected for the duration of the study.

13.2 Appendix 2: Contraceptive Guidance and Pregnancy Information Definitions:

Woman of Childbearing Potential

A woman is considered fertile following menarche and until becoming postmenopausal unless permanently sterile (see below).

If fertility is unclear (eg, amenorrhea in adolescents or athletes) and a menstrual cycle cannot be confirmed before the first dose of IP, additional evaluation should be considered.

Women in the following categories are not considered WOCBP:

- 1. Premenopausal female with 1 of the following:
 - Documented hysterectomy
 - Documented bilateral salpingectomy
 - Documented bilateral oophorectomy

For individuals with permanent infertility due to an alternate medical cause other than the above, (eg, Müllerian agenesis, androgen insensitivity), investigator discretion should be applied to determining study entry.

Note: Documentation can come from the site personnel's review of the participant's medical records, medical examination, or medical history interview.

- 2. Postmenopausal female
 - A postmenopausal state is defined as no menses for 12 months without an alternative medical cause.

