9.1.8. Medically Attended Adverse Events

Medically attended adverse events (MAAEs) is defined as an AE that results in a visit to a medical professional. Medically attended visits are defined as telemedicine visit, physician's office visit, urgent care visit, emergency room visit, hospitalization, or death. Scheduled study visits will not be considered medically attended visits. Medically attended adverse events related

to study vaccination are to be reported from the time of first study vaccination until completion of the participant's last study-related procedure, which may include contact for safety follow-up.

The percentage of participants with MAAE onset date within day 1-180 will be provided by dose group and by grade.

All MAAEs and treatment-related MAAEs with onset date within day 1-28 and within day 1-180 will be presented in separate summary tables for each dose and age group and total by SOC and PT. All MAAEs will be presented in a data listing by age group, dose group and participant number.

MAAEs will be reported in both listings and summaries from the time participant signs the ICF until exit from study (up to day 180 after the study vaccine administration, day 1-180).

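### Protocol 6.1.1.2 ends nonserious AE reporting at 28 days with no exception for MAAEs, although all MAAEs to about Day 180 are a primary endpoint

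*Protocol*

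**What the plan says.** **Endpoint.** Protocol Section 2, Table 2-1 lists as primary "Percentage of participants with MAAEs, SAEs, and AESIs from study vaccination through the end of the study", to about 180 days. SAP 2.1 repeats it. Neither restricts the events by seriousness or causality. Protocol 6.1.1.1.1 defines an MAAE as an AE leading to contact with a medical professional, telemedicine included, so an MAAE need not be serious.

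**Site instruction.** Protocol 6.1.1.2 opens with "Adverse events will be reported throughout the study". It then sets windows by class: "Nonserious AEs will be reported from the time of the administration of IP until 28 days after the administration of IP", and SAEs from ICF signature until study exit. MAAEs and AESIs are not mentioned.

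**Schedule of events.** Footnote m, in Protocol 13.1 and again in SAP 15.1, gives 28 days for unsolicited AEs and adds: "SAEs, MAAEs, and AESIs will be collected for the duration of the study". AE review is scheduled at every visit through Day 180 and at early termination.

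**SAP 9.1.8.** One sentence has as its subject MAAEs related "to study vaccination are to be reported from the time of first study vaccination". The same section defines MAAEs without reference to causality, tabulates all MAAEs and treatment-related MAAEs separately for Days 1-28 and Days 1-180, and lists and summarises MAAEs until study exit.

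**The concern.** Section 6.1.1.2 is where site staff would look for how long to record an event. Read on its own, it allows two classes: nonserious, closing at 28 days, and serious, continuing to exit. A participant who sees a physician on Day 60 for a nonserious complaint has an MAAE that counts toward the primary endpoint, yet falls outside the window in that section. A site could omit the event without believing that it had deviated.

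MAAEs have no second safeguard. The expedited-reporting section, 6.1.1.3.1, covers SAEs and AESIs only. Apart from the endpoint definition, the only place in the protocol that states the MAAE collection window explicitly is a table footnote.

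At stake is the completeness of one component of the primary safety endpoint. Events never entered cannot be recovered at analysis. If sites read the text differently and the mix of sites differs between dose groups, the dose-group percentages would also differ for reasons unrelated to dose.

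**Working it through.** **1. The windows side by side, for a nonserious event with onset on Day 60**

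| Source | MAAE | AESI |
|---|---|---|
| Protocol Table 2-1 (endpoint) | counted | counted |
| Protocol 6.1.1.2 | outside the 28-day window | outside the 28-day window |
| Protocol 13.1, footnote m | collected | collected |
| Protocol 6.1.1.3.1 (24-hour reporting) | not covered | required |
| Protocol 6.6 (confirmed SARS-CoV-2 infection) | not applicable | documented as an AESI |
| Protocol 13.4 (immune-mediated disease) | not applicable | expedited report, serious or not |

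The MAAE column contains a direct contradiction, with only the footnote and the endpoint on the other side. In the AESI column three specific rules override the general sentence.

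**2. Share of the endpoint window in conflict.** Taking the 28-day period as Days 1-28, as SAP 4 labels it: (180 − 28)/180 = 152/180 = 84.4%. Counting 28 full days after Day 1, so that the window ends on Day 29: 151/180 = 83.9%. Either way about 84%.

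**3. The plan's own detection figure.** Protocol 7.2 gives the chance of at least one AE among 30 participants as 78.5% at a 5% rate and 95.8% at 10%. The formula is 1 − (1 − p)^30:
- p = 0.05: 1 − 0.95^30 = 78.5%
- p = 0.10: 1 − 0.90^30 = 95.8%

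Both reproduce.

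**4. A bounding illustration, not an estimate.** The documents give no MAAE rates, so the Day-180 proportions q below are assumed. Further assumptions: constant hazard over 180 days, every event a nonserious MAAE, and every site applying 6.1.1.2 literally. The captured proportion is then c = 1 − (1 − q)^(28/180), and the chance of at least one recorded event in a dose group is 1 − (1 − c)^30.

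| Assumed q by Day 180 | Captured c | At least 1 in 30, full collection | At least 1 in 30, 28-day limit |
|---|---|---|---|
| 5% | 0.8% | 78.5% | 21% |
| 10% | 1.6% | 95.8% | 39% |
| 20% | 3.4% | 99.9% | 65% |
| 30% | 5.4% | about 100% | 81% |

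If sites follow footnote m, nothing is lost. The true position lies between the last two columns, and the documents do not say where.

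**The case against.** The strongest reply is that the protocol, read as a whole, makes its intent clear. Section 6.1.1.2 itself begins by saying AEs are reported throughout the study, and it has staff ask about changes in well-being at every visit. Sections 6.1.1.1.1 and 6.1.1.3 make the investigator responsible for AEs observed or reported during the study. Section 6.1 sends sites to the schedule of events, where footnote m gives the windows by type. On this reading the 28 days are simply the ordinary unsolicited-AE window.

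Much of this stands as evidence of intent. It does not remove the conflict, because the class-specific sentence follows the general one and divides events only into serious and nonserious.

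Three stronger readings are tempting, and the documents do not support them:

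- *Nonserious AESIs also stop at Day 28.* Protocol 6.1.1.1.4 says "An AESI (serious or nonserious) is defined as an AE or SAE of scientific and medical concern" and refers to 6.1.1.3.1, which states "Any AE that meets AESI criteria (Section 6.1.1.1.4) must be reported to PPD Pharmacovigilance within 24 hours", with no time limit. Section 6.6 says that confirmed infections "should be reported by the participant and documented as clinical events as well as AESIs", and schedules N-protein serology at Days 85 and 180. Appendix 13.4 requires an expedited report for any diagnosed immune-mediated disease. Mild COVID-19 and nonserious immune-mediated events are therefore covered after Day 28.
- *The SAP restricts the MAAE endpoint to related events.* It does not: 9.1.8 tabulates all MAAEs to Day 180, and SAP 4 and 8.1.1 use the same window without a causality limit. A SAP also does not instruct sites. The sentence is an internal inconsistency.
- *84% of the events are lost.* The figure counts days, not events.

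**Conclusion.** The concern holds for nonserious MAAEs. Protocol 6.1.1.2 contradicts the primary endpoint and footnote m over Days 29 to 180, about 84% of the endpoint window. This is exposure to conflicting instructions; no loss of events is shown, and the table of detection probabilities is a worst case on assumed rates. For AESIs the general sentence is imprecise, but the specific rules settle the matter. The design itself consistently runs to Day 180, so this is a wording conflict rather than a design flaw. It is worth correcting because it touches a primary endpoint and the correction is cheap.

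**What to change.** Reword the window sentence in Protocol 6.1.1.2 to name three classes, for example:

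- *Nonserious AEs that are neither MAAEs nor AESIs: from IP administration to 28 days afterwards.*
- *MAAEs and AESIs: from IP administration to study exit.*
- *SAEs: from ICF signature to study exit.*

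The start points matter. A shorter sentence that gave only the end dates would drop the existing ICF start for SAEs and the IP-administration start for nonserious events.

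As a secondary tidy-up, delete the qualifier limiting the one SAP 9.1.8 sentence to vaccine-related MAAEs. That sentence starts at first vaccination, whereas the last paragraph of 9.1.8 starts at ICF signature; the two should be aligned with the endpoint, which starts at vaccination.

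The cost is two edited sentences plus that alignment, with no data collection beyond what footnote m already requires. SAP 12 records that the study was closed early. If collection has ended, tabulate nonserious MAAE entries with onset after Day 28 by site, and state in the CSR which window sites applied. That would show whether the conflict affected recording, though it would not restore unrecorded events.

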6.1.1.2.1 Assessment of Severity

The severity, or intensity, of an AE refers to the extent to which an AE affects the participant's daily activities.

Solicited AEs will be graded in intensity by the participant. The investigator will assess the maximum intensity that occurred over the duration of the event for all unsolicited AEs, including SAEs, recorded during the study. The assessment will be based on the investigator's clinical judgment.

The intensity of the following solicited events will be assessed as described in Table 6-1.

Table 6-1 Intensity Scales for Solicited Symptoms

	1	T
.	Intensity	
Event	Grade	Parameter
Pain at administration site	0	None
	1	Mild: Any pain neither interfering with nor preventing normal
		everyday activities
	2	Moderate: Painful when limb is moved and interferes with
		everyday activities
	3	Severe: Significant pain at rest. Prevents normal everyday
D. I	0	activities
Redness at administration site	0	<2.5 cm 2.5 – 5 cm
	1	2.3 – 3 cm 5.1 – 10 cm
	2	
	3	>10 cm
Swelling at administration site	0	<2.5 cm
	1	2.5 – 5 cm and does not interfere with activity
	2	5.1 – 10 cm or interferes with activity
	3	>10 cm or prevents daily activity
Lymphadenopathy ^a	0	None
	1	Mild: No interference with activity
	2	Moderate: Some interference with daily activity
1	3	Severe: Prevents daily activity
Temperature ^b	0	<38.0°C or <100.4°F
	1	38.0 – 38.4°C or 100.4 – 101.1°F
	2	38.5 – 38.9°C or 101.2 – 102.0°F
	3	>38.9°C or >102.0°F
Headache	0	Normal
	1	Mild: Headache that is easily tolerated
	2	Moderate: Headache that interferes with normal activity
	3	Severe: Headache that prevents normal activity
Fatigue	0	Normal
	1	Mild: Fatigue that is easily tolerated
	2	Moderate: Fatigue that interferes with normal activity
	3	Severe: Fatigue that prevents normal activity
Myalgia	0	Normal
	1	Mild: No interference with daily activity
	2	Moderate: Interferes with daily activity
	3	Severe: Prevents daily activity
Arthralgia	0	Normal
	1	Mild: No interference with daily activity
	2	Moderate: Interferes with daily activity
	3	Severe: Prevents daily activity
Chills	0	None
	1	Mild sensation of cold; shivering; chattering of teeth
	2	Moderate tremor of the entire body; narcotics indicated
	3	Severe or prolonged, not responsive to narcotics

a. Defined as localized axillary, cervical or supraclavicular swelling or tenderness ipsilateral to the vaccination arm.

b. Refer to Section 6.1.4 for the definition of fever.

The intensity of AEs will be assigned to one of the following categories:

- Grade 1 (Mild): An AE that is easily tolerated by the participant, causing minimal discomfort, and not interfering with everyday activities.
- Grade 2 (Moderate): An AE that is sufficiently discomforting to interfere with normal everyday activities.
- Grade 3 (Severe): An AE that prevents normal, everyday activities. In adults, such an AE would, for example, prevent attendance at work and would necessitate the administration of corrective therapy.

An AE that is assessed as Grade 3 (severe) should not be confused with an SAE. Grade 3 is a category used for rating the intensity of an event; and both AEs and SAEs can be assessed as Grade 3. An event is defined as "serious" when it meets one of the predefined outcomes (Section 6.1.1.1.2).

Refer to Section 13.5 (Appendix 5) for grading of laboratory-associated AEs.

Changes in the severity of an AE should be documented to allow an assessment of the duration of the event at each level of intensity. Adverse events characterized as intermittent do not require documentation of onset and duration of each episode.

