5.8.2 Allowed Concomitant Therapy

Any concomitant medication deemed necessary for the welfare of the participant during the study may be given at the discretion of the investigator. However, it is the responsibility of the investigator to ensure that details regarding the medication are recorded in full in the eCRF.

The following concomitant therapies are allowed during the study:

- Acetaminophen/paracetamol
- Contraception, as described in Appendix 13.2
- Low-dose topical, ophthalmic, inhaled, and intranasal steroid preparations
- Local intra-articular steroids that are expected to remain localized in the joint space in which they are administered
- Inactivated influenza vaccines are allowed if received at least 14 days before or after study vaccination. Note: If other nonstudy vaccines are received during the study, participants may continue to complete the remaining study assessments. Any impact on the immunogenicity data will be addressed in the data analysis.

 Participants may take concomitant medications for management of medically stable chronic conditions as long as the medication and medical conditions are not exclusionary (Section 4.1.2)

Participants will be allowed to receive a booster dose of a licensed or authorized (conditional regulatory approvals, including emergency use authorizations are acceptable) COVID-19 vaccine, per national recommendations, if received after the Day 29 visit.

No concomitant medications will be provided by the sponsor or PPD.

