5.9 Study Holding Rules

The study holding rules in Table 5-2 will be applied independently to each dose group.

Table 5-2 Study Holding Rules

Study Holding Rule	Study Holding Rule Description	Number of Participants Needed to Trigger a Study Hold
1a	Death or any life-threatening SAE regardless of causality	≥1
1b	Any non-life-threatening SAE that cannot be reasonably attributed to a cause other than vaccination as per investigator or Sponsor assessment	≥1
1c	Any withdrawal from the study (by investigator or participant request) following a Grade 3 AE	≥1
1d	Any local or general solicited AE leading to hospitalization OR necrosis at the injection site; each with an event onset within the 7-day postvaccination period (Days 1 to 7)	≥1
1e	Severe cases of SARS-CoV-2 infection	≥2
1f	Any same or similar Grade 3 related unsolicited events, including but not limited to the identical MedDRA high-level term	≥2
1g	Same Grade 3 solicited local or systemic AE in an investigational group	>3
1h	Same Grade 3 or above abnormality in prespecified hematological or biochemical laboratory parameters with an event onset by Day 8 (± 1 day) postvaccination, except nonclinically significant lymphopenia	≥3
2a	Any Grade 3 solicited events in an investigational group, with an event onset within the 7-day postvaccination period (Days 1 to 7)	2 out of 3 first exposed participants 3 out of 5 first exposed participants 7 out of 16 first exposed participants 9 out of 22 first exposed participants 11 out of 28 first exposed participants 12 out of 30 first exposed participants (combined younger and older adult age groups)
2b	Any Grade 3 unsolicited AE , that can be reasonably attributed to the vaccination as per Investigator or Sponsor assessment, with an event onset within the 7-day (Days 1 to 7) postvaccination period	2 out of 15 first exposed participants 3 out of 30 first exposed participants (combined younger and older adult age groups)

Study holding rules 1a through 1d will be assessed by the investigators on a continuous basis. Study holding rules will lead to a halting of the entire study, with the exception of study

holding rule 1c, which will lead to halting of the concerned cohort and the next cohorts with higher doses.

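### Chills are graded by need for and response to narcotics, not by effect on daily activity, so Grade 3 chills can be under-counted in holding rules 1g and 2a, the Bayesian model and the severity summary

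*Protocol*

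**What the plan says.** Protocol Section 6.1.1.2.1 opens by saying that severity "refers to the extent to which an AE affects the participant's daily activities". It then says that "Solicited AEs will be graded in intensity by the participant". Table 6-1 sets the grades:

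- **Chills:** Grade 2 is "Moderate tremor of the entire body; narcotics indicated" and Grade 3 is "Severe or prolonged, not responsive to narcotics".
- **Headache, fatigue, myalgia, arthralgia, pain, swelling, lymphadenopathy:** Grade 3 includes prevention of activity; for fatigue it is "Severe: Fatigue that prevents normal activity".
- **Redness and temperature:** measured in centimetres or degrees.

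After the table, the same section gives general categories for AEs, including "Grade 3 (Severe): An AE that prevents normal, everyday activities". It does not exclude solicited events.

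On medication, Section 5.8.2 names acetaminophen/paracetamol among allowed therapies, lets the investigator give whatever the participant's welfare requires, and adds: "No concomitant medications will be provided by the sponsor or PPD".

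The grade is used in four places: holding rule 1g (the same Grade 3 solicited AE in more than 3 participants), holding rule 2a ("Any Grade 3 solicited events in an investigational group"), the Bayesian logistic regression in Appendix 13.3, and the SAP Section 9.1.4 summary by maximum severity.

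**The concern.** Chills is the only subjective solicited symptom whose Grade 3 has no activity criterion. A participant at home can say whether chills stopped normal activity. The same participant cannot readily judge whether a narcotic was indicated, and cannot observe a failed response to a drug that was never taken. A participant kept in bed by chills who took no narcotic is Grade 3 under the general category but, read literally, not under Table 6-1.

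The grade matters because Grade 3 solicited events drive the reactogenicity holding rules and the model that guides escalation against a 30% tolerable rate. With 30 participants per dose group, one or two misgraded participants can move these signals. Protocol Section 3.2 reports that the severity of systemic events rose with dose for the first-generation vaccine. It is therefore plausible, though not shown, that any loss would be larger at the higher doses.

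**Working it through.** **Inputs from the documents.** There are 30 participants per dose group. Rule 1g triggers at more than 3, that is at least 4. Rule 2a triggers at 2/3, 3/5, 7/16, 9/22, 11/28 or 12/30. Appendix 13.3 supplies the model, priors, 30% limit and 50% guide.

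**Assumptions.** The documents give no chills rate. The proportion of participants whose only Grade 3 event is chills, and is missed, is set at m = 2%, 5% or 10%. For rule 1g, the rate q of activity-preventing chills is set at 5% to 20%. Events are treated as independent, and rule 2a as checked at its six stated counts.

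**1. Reproduce the plan's model.** logit p(d) = α + β·ln(d/12), with the stated 80/20 mixture prior and no age effect (as the table note says). The prior means follow from the stated rates: logit(0.30) = −0.8473 and ln[(logit 0.30 − logit 0.10)/ln 3] = 0.2060. The posterior was found by grid integration, with 0/30 at 2 µg entered as 1/30 following the convention under Table 13-2. Scenario 2, probability that the next-dose rate exceeds 30%:

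| Next dose | Computed | Table 13-2 |
|---|---|---|
| 8 µg | 0.240 | 0.236 |
| 12 µg | 0.441 | 0.437 |
| 16 µg | 0.653 | 0.645 |
| 20 µg | 0.994 | 0.994 |

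All agree within 0.01. The printed current-dose value at 4 µg (0.050) does not reproduce (about 0.000), but it is not used here.

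**2. Remove chills-only participants at 12 µg in scenario 2.**

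| Counted at 12 µg | P(16 µg rate > 30%) |
|---|---|
| 8/30 | 0.653 |
| 7/30 | 0.533 |
| 6/30 | 0.408 |

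Two lost participants cross the 50% guide. Losing one at 8 µg and one at 12 µg also crosses it (0.458). Without the 0-to-1 replacement the values for 8, 7, 6 and 5 events are 0.751, 0.639, 0.514 and 0.386, so three losses at 12 µg would be needed; that version does not match Table 13-2.

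**3. Rule 2a.** With a true any-Grade-3 rate p, the recorded rate is p − m. The trigger probability is the sum over looks of the probability of first reaching the threshold there, from exact binomial increments. First look at p = 0.30: 3(0.30²)(0.70) + 0.30³ = 0.216. With m = 5% the recorded rate is 0.25: 3(0.25²)(0.75) + 0.25³ = 0.156. Over all six looks:

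| True rate | m = 0 | 2% | 5% | 10% |
|---|---|---|---|---|
| 30% | 0.407 | 0.340 | 0.251 | 0.141 |
| 40% | 0.757 | 0.694 | 0.589 | 0.407 |

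**4. Rule 1g for chills.** P(X ≥ 4) = 1 − Σ C(30,k) q^k (1−q)^(30−k), summed over k = 0 to 3. This is 0.061, 0.353, 0.678 and 0.877 at q = 5%, 10%, 15% and 20%. If no such event is graded 3, it is 0.

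**The case against.** A reader might infer that disabling chills necessarily vanish from a Grade 3 endpoint and from every escalation rule. The documents do not support that.

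- **No Grade 3 endpoint exists.** The primary endpoint counts each solicited AE at any grade, so all chills stay in it. Severity enters through the SAP summary.
- **Rule 2a and the model count any Grade 3 solicited event.** A participant with another Grade 3 symptom still counts.
- **The wording is ambiguous.** The word severe in the chills row can be read as standing alone, and the general category would make the event Grade 3. The eDiary screen text is not in the documents.
- **Narcotics are not barred.** Section 5.8.2 permits any medication the investigator considers necessary.
- **The investigator can re-grade.** SAP Section 9.1.4 replaces the eDiary grade in the summaries when the investigator judges it too high or too low.
- **Decisions are not mechanical.** The 50% figure is a guide, the Safety Review Team sees all safety data, and medical judgment decides.

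These points stand and limit the claim, but they do not remove it. Ambiguity means that identical events can be graded differently. An investigator re-grading by Table 6-1 meets the same narcotic wording, and the SAP does not say that the corrected grade reaches the holding rules or the model. Nothing offsets the loss in rule 1g, because another symptom cannot stand in for chills.

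SAP Section 12 also says that the study closed early, so a revised table may reach few participants. That makes the handling of existing data more important.

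**Conclusion.** The chills row conflicts with the section's own definition of severity, with the other subjective symptoms and with the general Grade 3 category. Taken literally, it can under-count Grade 3 chills. Rule 1g is most exposed; rule 2a and the model are exposed only through chills-only participants; the maximum-severity summary is exposed unless the investigator re-grades; the primary endpoint is not.

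The true size is unknown. It rests on assumed chills rates, on the literal reading and on no corrective re-grading. Under those conditions a 5-point loss lowers the chance of triggering rule 2a by 0.407 − 0.251 = 0.156 at a true 30% rate, and by 0.757 − 0.589 = 0.168 at 40%. A 2-point loss costs about 0.06 to 0.07. Two participants are enough to move the scenario 2 signal across the guide. That is enough to justify correcting one table row, but not to conclude that any dose was wrongly judged tolerable.

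**What to change.** 1. Reconcile the chills row of Table 6-1 with Section 6.1.1.2.1, so that chills, like the other subjective symptoms, are graded on interference with or prevention of daily activity. Match any eDiary text.
2. State that the investigator-corrected severity in SAP Section 9.1.4 also feeds rules 1g and 2a and the Bayesian model.
3. For participants already graded under the narcotic wording, flag this in the clinical study report. Add a sensitivity summary of any Grade 3 solicited event, using investigator re-graded chills or counting Grade 2 chills as Grade 3 as an upper bound. A summary that only leaves chills out would remove the events in question.

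The cost is one table row, matching diary text, one sentence on the data source and one supportive table. Chills grades before and after the change will not be directly comparable, and slightly more Grade 3 events may be counted.
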